Relevance to future decision-making in both clinical trials and clinical practice. The major relevance of this work will be to the design of future clinical trials that use AD biomarkers such as amyloid as part of the inclusion criteria and the translation of their results into clinical practice. If we demonstrate substantive cognitive bias, the sample size of future trials may need to be increased, and sub-analyses of our data (not described in this proposal) could guide us to select tests or batteries of tests that are less vulnerable to stereotype bias. If we demonstrate that there are individuals who become anxious or severely distressed in response to learning their amyloid status, future trials may require processes for recognition and treatment of such symptoms. While our recruitment procedures will not result in a subject pool that is representative of clinical practice, these insights will also be relevant to guide clinicians in ordering and communicating results of amyloid imaging to cognitively normal individuals. Our study is not designed to formally measure costs or resource utilization, but will measure the degree to which subjects seek consultation and order additional diagnostic tests after obtaining amyloid imaging. This information will help researchers and clinicians begin to understand the downstream implications of amyloid imaging as it becomes increasingly utilized.

II. Specific Aims

We will enroll 370 cognitively normal individuals, aged 65-80, using *APOE* genotyping with oversampling of $\epsilon 4+$ individuals to enrich the enrollment sample such that roughly 30% of those scanned will be amyloid elevated (A+) and the remainder amyloid not elevated (A-). From this enriched sample, 370 participants (approximately 25% African American) will all receive their Alzheimer's Disease Dementia Risk Disclosure and be randomized (50/50) to either receive their amyloid scan results (Disclosure or D+) at the disclosure visit or not at the disclosure visit (D-). Those in the D- group will receive their amyloid scan results at an additional visit at the end of the study. The primary cognitive outcome will be the A4 Study's Preclinical Alzheimer Cognitive Composite and the primary outcome for psychological distress will be the Impact of Events Scale (IES). We plan the following analyses:

Specific Aim #1: To determine whether disclosure of elevated brain amyloid will bias ADCS-Preclinical Alzheimer Cognitive Composite (ADCS-PACC) test results.

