Analyses of IES as the main secondary outcome and of other measures, will be conducted in a similar fashion. While our main focus for the IES will be upon the contrast between the A+D+ and A-D+ groups, we will also contrast the A+D+ and the D- groups (as long as the A+D- and A-D- exhibit similar outcomes). The D- group may experience increased distress waiting for the disclosure of their imaging, which could reduce our power to explore comparisons between A+D+ and D- groups, although we did not see this occurring in our prior REVEAL studies when participants in the non-disclosure arms were waiting for their genotype data at the end of the study. It will also be of interest to compare the difference between A+D- and A-D- groups, because this comparison would reveal any differences in cognition due to the amyloid burden

itself among participants who do not learn their amyloid status at the fourth visit. We do not expect to find any difference here in only 6 months of follow-up. For Exploratory Aims 1.2 and 2.3, we will examine regression models or MMRM models with interaction terms for race and group to evaluate whether the differences at 6 months between the groups (e.g. A+D+ vs A+D-) are similar for AAs and non-AAs. Point estimates will be considered in addition to confidence intervals and p-values.

For the 6-month follow-up visit digit-span task, we will examine whether working memory performance and pupil dilation responses differ when under high than low threat differentially depending on both disclosure status and amyloid levels.

For the 6-month visit digit-span task, we will examine whether working memory performance and pupil dilation responses differ when under high than low threat differentially depending on both disclosure status and amyloid levels.

Power Calculation

Our objective is to achieve 80% power to detect a difference of moderate effect size (0.4-0.6 SD units) on the primary outcome of ADCS-PACC mean score between the A+D- and A+D+ groups at 6 months.

Assuming a PACC standard deviation of 2.2⁴⁴, 50 individuals per group would provide 80% power to detect a difference of 1.25 PACC units (0.52 SD units) between A+D- and A+D+ at 6 months.

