Exploratory Analysis 1.3: The analysis will be the same as the primary analysis, but now conducted only in the African Americans in the study. If the hypothesis is true, we expect a larger difference, but the study is not powered for this subgroup analysis. To formally test whether African Americans have a greater response, we will perform analyses of the full group of A+ individuals, adding an interaction term to the model for race * disclosure group.

Aim 2: To determine whether disclosure of elevated brain amyloid will cause psychological distress.

Study Subjects: All Study Participants and the subgroup of A+ subjects

Outcomes: IES (Impact of Event Score), measured twice (6 wks., 6 mos.), and INI-AD, measured twice (6 wks., 6 mos.)

Hypothesis 2.1: At 6 weeks after disclosure, A+D+ participants will have greater IES scores and INI-AD scores than A-D+ or D- participants.

Analysis 2.1: Analysis will generally use the same methods as Aim 1. For this Aim, IES is the primary outcome for which we will use an alpha level of 0.05. INI-AD is a secondary outcome. Our main focus for this aim is contrasting scores between the A+D+ and A-D+ groups. We will also contrast the A+D+ and the D- groups (as long as the A+D- and A-D- exhibit similar outcomes). As in Aim 1, we will obtain

descriptive statistics between the two groups (A+D- and A-D+ for the first contrast and then A+D- vs the D- group). We will also evaluate the confounding effect of Covid-19 as described in Aim 1 and subsequently other potential confounders for these contrasts and incorporate if needed in further regression analyses. Note that there is no IES at baseline. So there is no adjustment for a baseline measure. The same holds true for INI-AD. One major difference here is that the IES and INI-AD are not normally distributed and cannot be transformed to become so. Thus, we will use generalized linear models fit with generalized estimating equations using a log link and a gamma distribution. If needed, we will add a value of 1 to all scores to shift the distribution away from zero and use a log transform on the data. We will focus on the differences at 6 weeks, but also evaluate the time-averaged differences.

Exploratory Hypothesis 2.2: Comparison of outcomes at 6 weeks and 6 months after disclosure will show African Americans to be equally vulnerable to psychological distress as measured by IES and INI-AD after amyloid imaging compared to all other racial and ethnic groups.

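### SAP Analysis 2.1 writes A+D- where A+D+ is needed in both descriptive pairs, so the Aim 2 descriptive comparison omits the participants told of elevated amyloid

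*SAP*

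**What the plan says.** Analysis 2.1 in the SAP (Aim 2) first names its contrasts. The main one is given as "Our main focus for this aim is contrasting scores between the A+D+ and A-D+ groups". The second follows: "We will also contrast the A+D+ and the D- groups (as long as the A+D- and A-D- exhibit similar outcomes", the condition being that the two non-disclosed cells look alike.

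The groups for the descriptive step come next: "descriptive statistics between the two groups (A+D- and A-D+ for the first contrast and then A+D- vs the D- group". The sentence after that turns to Covid-19 and then to "other potential confounders for these contrasts and incorporate if needed in further regression analyses".

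Other places name the index group consistently. SAP Hypothesis 2.1 states that "A+D+ participants will have greater IES scores and INI-AD scores than A-D+ or D- participants". The protocol (Section VI, Data Analysis) says "our main focus for the IES will be upon the contrast between the A+D+ and A-D+ groups" and adds "we will also contrast the A+D+ and the D- groups (as long as the A+D- and A-D- exhibit similar outcomes". Protocol Section II, Secondary Hypothesis 2.1, also has A+D+ as the index group. It sets a different time point from the SAP, which is a separate matter.

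The meaning of D- is clear from Protocol Section II: "Those in the D- group will receive their amyloid scan results at an additional visit at the end of the study". A+D- participants therefore do not know their result when the 6-week and 6-month data are collected.

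**The concern.** The parenthesis says that its pairs serve the first and second contrasts, but A+D- is the index group of neither. The first written pair differs in both amyloid status and disclosure, so it isolates neither. The second compares a subgroup with a group that includes it.

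Two things could follow. The Aim 2 descriptive table would not show the group that the aim is about. The choice of covariates could also be affected. Analysis 2.1 takes its general methods from Aim 1, and SAP Primary Analysis 1.1 uses the two-group comparison to select confounders: those that differ at p < 0.05 enter the regression. If the Aim 2 screen is run on the written pairs, it is run on the wrong people.

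Covariate choice carries more weight here than in Aim 1. A+D+ versus A-D+ compares amyloid groups within one arm, so randomisation does not balance it, and A+D+ versus D- also mixes amyloid status. Protocol Section III describes age as strongly related to amyloid positivity. The SAP notes that the IES has no baseline value, so baseline adjustment cannot offset an imbalance.

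**Working it through.** The plan states no figure for these pairs, so there is none to reproduce. The check is one of group membership, with expected sizes for scale.

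**Step 1: labels side by side.** There are four cells: A+D+, A+D-, A-D+ and A-D-. The D- group is A+D- plus A-D-.

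| Contrast | As stated | Descriptive pair as written | Pair after correction |
|---|---|---|---|
| First | A+D+ vs A-D+ | A+D- vs A-D+ | A+D+ vs A-D+ |
| Second | A+D+ vs D- | A+D- vs D- | A+D+ vs D- |

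The written pairs together cover A+D-, A-D+ and A-D-. The only cell missing is A+D+. In the second written pair, A+D- is on both sides. After correction, neither pair overlaps and all four cells are covered.

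**Step 2: expected sizes.** Inputs:
- 370 enrolled and about 10% dropout (Protocol Section VI, Power Calculation)
- 1:1 allocation (Protocol Section V, Step 7)
- 25% to 30% A+ (SAP, the paragraph on not reaching the planned sample size; Protocol Section II gives roughly 30%)

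Completers: 370 × 0.90 = 333. Per arm: 333 / 2 = 166.5.

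| A+ share | A+D+ (= A+D-) | A-D+ | D- | A+D- as share of D- |
|---|---|---|---|---|
| 25% | 166.5 × 0.25 = 41.6 | 166.5 × 0.75 = 124.9 | 166.5 | 41.6 / 166.5 = 25% |
| 30% | 166.5 × 0.30 = 50.0 | 166.5 × 0.70 = 116.6 | 166.5 | 50.0 / 166.5 = 30% |

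About 42 to 50 A+D+ completers are left out of the written pairs. The corrected pairs would be about 42 vs 125 and 42 vs 167 at 25% A+, or about 50 vs 117 and 50 vs 167 at 30%.

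**Step 3: could the wording be intended?**
- It is not the check that A+D- and A-D- behave alike before pooling. That check needs A-D- alone as comparator, and neither pair has it.
- Protocol Section V, Step 7 swaps the arm names attached to D+ and D-, but still describes D+ as learning the result at Visit 4 and D- as not learning it. The swap does not turn A+D- into the disclosed group.

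**The case against.** The strongest reply is that this is a slip of the pen which the paragraph corrects by itself. The parenthesis refers back to contrasts correctly defined in the sentences before it. The second written pair is so plainly unusable that a careful analyst would notice. The later reference to the contrasts, in the confounder sentence, reads naturally as meaning the stated ones. All of this is fair, and it limits the consequence. It does not make the sentence right, and an analysis plan should not depend on the reader to repair group labels.

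Three stronger readings are tempting, and the documents do not support them.
- *A reader might infer that the SAP tests the wrong distress contrast.* It does not. The parenthesis governs the descriptive step only; the hypothesis and the contrasts to be tested name A+D+.
- *A reader might infer from the repeated label that the choice was deliberate.* One label mistyped twice in one parenthesis fits a single drafting slip equally well.
- *A reader might infer that imbalance in Covid-era visits would go unadjusted.* The SAP's Covid-19 paragraph under Aim 1 puts actual visit time and a post-15-March-2020 indicator into the primary analysis without a group-difference screen, and Analysis 2.1 refers back to it. Analysis 2.1 does leave some room by saying that confounders enter if needed.

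Three further mitigations stand. SAP Primary Analysis 1.1 already describes D+ and D- among A+ subjects, so A+D+ is described somewhere. The protocol's Data Analysis text lists sex, age and APOE genotype as adjustment factors and treats the IES similarly, although the SAP makes age conditional on the screen. Finally, disclosure is randomised, so A+D- and A+D+ have the same expected baseline profile. A screen on the first written pair would on average see the same baseline imbalance as the correct one. The two would disagree through chance differences between A+D- and A+D+, which can matter at about 42 to 50 per cell.

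**Conclusion.** The inconsistency is real and can be verified within one paragraph: both descriptive pairs in Analysis 2.1 carry A+D- where A+D+ is required. Followed literally, this gives a wrong Aim 2 descriptive table, without about 42 to 50 expected A+D+ completers and with a second comparator of which 25% to 30% is the index group itself. Confounder screening in the wrong groups, for example on age, is possible but not certain. It arises only if the confounder sentence is read as pointing to the mislabelled pairs.

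The IES contrasts, the model and the 0.05 alpha level are not affected. The sizes assume 370 enrolled, 10% dropout that is even across cells, equal allocation and the same A+ share in each arm. The 25% to 30% overlap shows that the written pair is unusable; it does not measure bias in any planned estimate. The point deserves correction because covariate choice may rest on it, but it is a small one.

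**What to change.** In SAP Analysis 2.1, change A+D- to A+D+ in both positions of the parenthesis, so that the descriptive pairs are A+D+ with A-D+ for the first contrast and A+D+ with D- for the second. Add one clause stating that the Covid-19 and other confounder evaluation is carried out on those same pairs.

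The cost is one line of SAP wording. No hypothesis, test, model, alpha level or sample size changes. Exploratory Analysis 2.2, which reuses the methods of Analysis 2.1, is corrected at the same time.

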The first neuropsychological test battery will be performed at this Visit #2. Baseline cognitive status will be ascertained using the Alzheimer's Disease Cooperative Study Preclinical Alzheimer Cognitive Composite (ADCS-PACC) to ensure the participant is cognitively normal.⁴⁴ The ADCS-PACC is comprised of measures of episodic memory (Buschke Selective Reminding Test, Logical Memory I, II), timed sensorimotor function (Digit Symbol Subtest from the WMS), and a global test of cognition (MMSE). Pre-specified cut-off scores of safety screening measures are listed under the "Safety of Participants" section below.

In addition to the ADCS-PACC, the neuropsychological test battery is also comprised of 1) a test of effort: Test of Memory Malingering (TOMM)⁴⁵, 2) a measure of attention and short-term memory capacity: Digit Span forward span test⁴⁶ and 3) a test of premorbid function (TOPF)⁴⁷

After the neuropsychological battery is the full education session. To assess participants' knowledge prior to the education session, we will ask the participant a list of questions on a "Pre-Education" checklist. Participants will then receive a full educational session about Alzheimer's disease dementia risk factors, amyloid imaging, and the meaning of an elevated and not elevated result in an older adult with normal cognition. The content of this written description was generated using a modified Delphi consensus process that involved experts in human amyloid imaging and informed consent for genetic testing. It includes sections that describe what is amyloid, what is Alzheimer's disease, how do we know whether someone has brain amyloid, what does having a brain amyloid scan involve, what does a positive brain amyloid scan mean, is a positive amyloid scan like other medical risks, and what a negative brain amyloid scan means. The participant is allowed to ask questions regarding the information just learned. After the educational session, the participant will complete a "Post-Education" checklist.

The NEO personality index,⁴⁸ Geriatric Depression Scale (GDS),⁴⁰ Mini-State Trait Anxiety Inventory (Mini-STAI),⁴¹ and Columbia Suicide Severity Rating Scale (CSSRS),⁴² are then administered to the participant to assess for signs of depression and anxiety (see "Inclusion/Exclusion Criteria" section for cut-off scores).

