Eyetracking data and questionnaire data from the 6-month follow-up visit related to stereotype threat and the digit span task will be analyzed by the University of Southern California (USC) team. All data will be de-identified before being sent to USC for analysis. Each site will upload their de-identified, raw pupillometry data (labeled with subject ID#) to the BU secure Web data repository and from there it will be sent to USC.

Data Analysis

The analytical strategy will focus on comparing A+D+ and A+D- groups on the ADCS-PACC score at 6 months to better identify if non-disclosure itself had an effect on ADCS-PACC performance. Although the primary comparison is not based on the fully randomized groups, it is a comparison of randomized groups in the pre-specified subgroup of A+ subjects, thus controlling for type 1 error. The power calculation is based on the comparison within the subgroup of A+ subjects, so type 2 error is also controlled. Our primary analysis will use a mixed-effects model repeated measures (MMRM)⁵⁷ approach to evaluate the three repeated measures over time. This Intention-to-Treat (ITT) analysis will incorporate information from those who drop out over the 6 months, assuming missing at random, and have better control of type 1 error and power. We will model time as a categorical measure, and the primary outcome will be the estimated difference (contrast) between the two groups at 6 months. As randomization may not be fully successful in balancing confounding factors between the groups (subgroups of the randomized groups), the analysis will also adjust for potentially confounding measures such as sex, age and *APOE* genotype. We will also include the baseline measure of the ADCS-PACC score in one regression model (using the two repeated measures at 6 weeks and 6 months) to allow for differences in cognitive functioning at baseline. We will also consider models that examine change from baseline, with and without adjustment for the baseline measure.

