Primary Analysis 1.1: For this aim we focus on one outcome, ADCS-PACC, and thus use an alpha level of 0.05 to determine statistical significance. First, we will obtain descriptive statistics for those who are in the D+ and D- groups among A+ subjects. Then, we will compare ADCS-PACC scores between D+ and D- groups among A+ subjects using a two-sided test of means. Next, we will compare D+ and D- groups on potential confounders. We will initially consider confounders due to the Covid-19 pandemic (as described below) and then consider other confounders (including age, education, premorbid function, experiences of discrimination). If any are significantly different between the two groups ($p < 0.05$), despite randomization, we will conduct regression analysis adjusting for those confounders that are different. Analyses will be repeated measures (6 wks. and 6 mos.) adjusting for baseline measure at time of randomization. We will focus on 6 month differences, but also check for time-averaged differences between D+ and D- groups. Check ADCS-PACC for normality. If normal, linear regression analysis for repeated measures can be used, specifically a mixed-effects model with repeated measures (MMRM). If not normal, we will use an appropriate transformation to make the distribution more normal. We will also conduct an Intention-to-Treat (ITT) analysis, which will incorporate information from those who drop out over the 6 months, assuming missing at random. This analysis will have better control of type 1 error and power. We will model time as a categorical measure, and the primary outcome will be the estimated difference (contrast) between the two groups (D+ and D-) at 6 months and secondarily the time-averaged difference. We will also apply a model with 3 repeated measures (baseline, 6 wks., 6 months) without adjustment for baseline ADCS-PACC to examine the full trend over time, but this will be a secondary analysis.

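### The IES and INI-AD models pre-specify no adjustment for baseline mood; GDS, mini-STAI or NEO can enter only through a significance-triggered confounder step

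*SAP*

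**What the plan says.** SAP, Aim 2, Analysis 2.1, makes IES the primary outcome of the aim at alpha 0.05, with INI-AD secondary. The main contrast is A+D+ against A-D+, with the focus on 6 weeks. On covariates it says three things:

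- The general approach is inherited: "Analysis will generally use the same methods as Aim 1".
- After Covid-19, the analysts will evaluate "subsequently other potential confounders for these contrasts and incorporate if needed in further regression analyses".
- On baseline values: "Note that there is no IES at baseline. So there is no adjustment for a baseline measure. The same holds true for INI-AD".

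The inherited rule is in SAP, Primary Analysis 1.1. The named candidates are "other confounders (including age, education, premorbid function, experiences of discrimination", an open list. The trigger for adjusting is "If any are significantly different between the two groups", with p < 0.05 as the threshold.

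The protocol's Data Analysis section has no such trigger: "the analysis will also adjust for potentially confounding measures such as sex, age and *APOE* genotype". It then says IES will be handled similarly. That list is also open and also names no mood or personality measure.

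Protocol, Section V, Step 5 (Visit #2) lists the NEO, GDS, mini-STAI and CSSRS, which "are then administered to the participant to assess for signs of depression and anxiety". The scan and randomisation come at Visit #3 and disclosure at Visit #4. GDS and mini-STAI are also given at Visit #1.

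**The concern.** The absence of a baseline IES or INI-AD does not mean that the trial lacks baseline information on proneness to distress. Three relevant instruments are already in the database for everyone who reaches the scan. Two things are at stake.

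The first is precision. If mood before disclosure predicts IES after disclosure, leaving it out gives a wider interval than necessary for the main secondary outcome. The A+D+ group is small.

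The second is comparability. Only disclosure is randomised. A+D+ against A-D+ compares amyloid groups within the disclosed arm, so randomisation does not protect it against differences in prior mood. The other stated contrast, A+D+ against all D-, also sets an A+ group against one of mixed amyloid status. Aim 1 adjusts for the outcome's own baseline in a comparison that is randomised within A+. Aim 2, whose main comparison is not randomised, commits in advance to no corresponding covariate.

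**Working it through.** **Plan figures.** The documents give no SD, power or sample size for IES or INI-AD, so there is no Aim 2 figure to reproduce. As a check on method, the SAP's Aim 1 detectable difference of 1.2451 (50 per group, SD 2.2 from the protocol, 80% power, two-sided 0.05) comes out as 1.2449 with a noncentral t calculation. The same method is used below.

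**Group sizes** (protocol, Power Calculation: 370 enrolled, about 10% dropout; 1:1 allocation; A+ share about 30% in protocol Section II, 25% to 30% in the SAP):
- Disclosed completers: 370 × 0.9 / 2 = 166.5.
- At 30% A+: 166.5 × 0.30 ≈ 50 A+D+, leaving about 117 A-D+.
- At 25% A+: 166.5 × 0.25 ≈ 42 A+D+, leaving about 125 A-D+.

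**Standard error of A+D+ against A-D+, in SD units:** √(1/n₁ + 1/n₂).
- 50 and 117: √(0.0200 + 0.0085) = 0.169.
- 42 and 125: √(0.0238 + 0.0080) = 0.178.

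**How often a p < 0.05 screen would flag a true mood difference** (two-sided t test):

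| True difference | 50 vs 117 | 42 vs 125 |
|---|---|---|
| 0.2 SD | 22% | 20% |
| 0.3 SD | 42% | 39% |
| 0.4 SD | 65% | 61% |

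Analysis 2.1 focuses on 6 weeks, when fewer participants may have dropped out. With no dropout at all, 370 / 2 = 185 disclosed gives about 56 and 129 at 30% A+. The 0.3 SD difference is then flagged 46% of the time, so the conclusion does not depend on the dropout figure.

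**Precision from a fixed mood covariate.** Let r be the correlation of baseline mood with later IES. The documents do not give it, so r is an assumption. In a linear model the standard error is multiplied by √(1 − r²), and the equivalent gain in sample size is 1/(1 − r²) − 1. Without adjustment, the detectable difference at 80% power with 50 and 117 is 0.476 SD.

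| r | SE factor | SE reduction | Equivalent extra participants | Detectable difference |
|---|---|---|---|---|
| 0.2 | 0.980 | 2% | 4% | 0.467 SD |
| 0.3 | 0.954 | 5% | 10% | 0.454 SD |
| 0.4 | 0.917 | 8% | 19% | 0.436 SD |
| 0.5 | 0.866 | 13% | 33% | 0.412 SD |

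The planned model is a gamma GEE with a log link, so these figures are approximate.

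**Hypothetical bias.** If A+ and A- differed systematically by g SD in baseline mood, the unadjusted contrast would shift by g × r. For g = 0.3 and r = 0.3 the shift is 0.09 SD, about half the standard error (0.09 / 0.169 = 0.53). For g = 0.2 and r = 0.2 it is 0.04 SD, about a quarter (0.04 / 0.169 = 0.24). Both g and r are assumed.

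**The case against.** A reader might infer from the quoted sentences that the IES and INI-AD models have no baseline adjustment of any kind. The documents do not say that. The sentences rule out only adjustment for the outcome's own baseline, which does not exist. The sentence before them provides for other confounders, the candidate list is open and so could admit mood, and the protocol extends adjustment for measures such as sex, age and APOE genotype to IES without a significance test. All of this stands. What remains is that mood is not named and that the SAP's route to including it is a test.

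A reader might also infer that the main distress contrast is biased by prior mood. The documents do not support that either. Mood is measured before anyone learns a result, so the result cannot have caused a baseline difference, and nothing in the documents points to a systematic one. A chance difference of 0.2 SD is only about 1.2 of its own standard errors (0.2 / 0.169) and is already reflected in the unadjusted standard error, so it should not be counted again as bias. The plan's check that A+D- and A-D- have similar outcomes would tend to reveal a systematic mood effect, though imperfectly, because that arm receives different information.

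Finally, screening excludes GDS above 10 and STAI of 19 or more, which narrows the mood range and probably lowers both r and any imbalance. That favours the lower rows of the precision table. It does not remove the case for adjustment, since scores up to those limits can still be enrolled.

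**Conclusion.** The point holds as a gap in pre-specification. No mood or personality covariate is fixed for IES or INI-AD, and the only route in is a test that would miss a 0.3 SD difference more often than not (about 58% of the time with 50 and 117 completers). A screen on imbalance is also the wrong tool for precision, because it ignores whether the covariate predicts the outcome. It leaves the final model to be settled after the data are seen.

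The benefit is modest and uncertain: a standard error lower by 2% to 13% for r between 0.2 and 0.5, on a linear approximation. Protection against confounding is a precaution, not the correction of a demonstrated bias. The absence of the covariates is certain; the size of the gain is not. This is a free improvement, not a flaw that threatens the Aim 2 result.

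**What to change.** Keep the statement that IES and INI-AD have no baseline value, since it is correct, and add after it in Analysis 2.1:

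*All IES and INI-AD models include Visit 2 mini-STAI and GDS as fixed covariates, regardless of any baseline significance test, in addition to the other planned covariates.*

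NEO may be added as a sensitivity analysis. Other sets of mood covariates would also be defensible; what matters is that the set is fixed before the outcome data are examined. With the planned log link, the ratio of means keeps its interpretation in contrasts that are randomised, such as D+ against D- within A+.

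The cost is one SAP sentence and two model parameters. No new data or visits are needed.
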